6.5.2 Unbound Plasma LOXO-292 Pharmacokinetic Parameters

An analysis to determine the unbound plasma LOXO-292 PK parameters will be conducted. The fraction of unbound (fu) LOXO-292 in plasma for each subject will be estimated via an ex vivo protein binding analysis using a predose plasma sample. Unbound plasma concentrations of LOXO-292 will be calculated by multiplying the measured plasma concentrations by the fraction unbound of each subject (Cu = measured concentration x fu) at each sampling time point for that subject. The following unbound PK parameters using the individual Cu values and actual sampling times using Phoenix[®] WinNonlin[®] Version 7.0 or higher:

Table 6.2. Noncompartmental Plasma Pharmacokinetic Parameters to be Calculated for Unbound LOXO-292

Label to be Used in the Text, Tables and Figures	Definition	Method of Determination
AUC0-t,u	Area under the concentration-time curve for unbound LOXO-292 concentration from time 0 to the time of the last observed non-zero	Calculated using the Linear Trapezoidal with Linear Interpolation Method
AUC0-inf,u	Area under the concentration-time curve for unbound LOXO-292 concentration from time 0 extrapolated to infinity	Calculated as AUC0-t,u + (Clast,u/Kel,u) where Clast is the last observed/measured unbound concentration
Cmax,u	Maximum observed unbound LOXO-292 concentration	Taken directly from unbound plasma concentration of LOXO-292
Kel,u	Apparent terminal elimination rate constant; represents the fraction of unbound drug eliminated per unit time	Calculated as the negative of the slope of a linear regression of the log(unbound concentration)-time for all unbound concentrations >LLOQ during the terminal elimination phase
CL/F,u	Apparent total plasma clearance of unbound LOXO-292 after extravascular (oral) administration	Calculated as Dose/(AUC0-inf,u)
Vz/F,u	Apparent volume of distribution of unbound LOXO-292 during the terminal elimination phase after extravascular administration	Calculated as Dose/(AUC0-inf,u x Kel,u*)

* The same timepoints selected for the calculation of Kel will be selected for the calculation of Kel,u. Kel,u will be calculated in WinNonLin but will not be presented in tables.

Unbound PK parameters will not be calculated for subjects with fewer than 3 consecutive postdose time points with quantifiable concentrations. Subjects for whom there are insufficient data to calculate the PK parameters will be included in the concentration tables only and excluded from the statistical analysis.

For the calculation of the unbound PK parameters, plasma concentrations BLQ prior to the first quantifiable concentration will be set to 0 and plasma concentrations BLQ after the first quantifiable concentration will be treated as missing.

The $K_{el,u}$ will be determined using linear regressions composed of least 3 data points. The $K_{el,u}$ will not be assigned if 1) the terminal elimination phase is not apparent, 2) if $T_{max,u}$ is one of the 3 last data points, or 3) if the R^2 value is less than 0.75. In cases where the $K_{el,u}$ interval is not assigned, the values of $t_{1/2,u}$, $AUC_{0-inf,u}$, $CL/F,u$, and $Vd/F,u$ are considered not calculable and will not be reported. Wherever the resulting $t_{1/2,u}$ is more than half as long as the sampling interval, the $K_{el,u}$ values and associated parameters ($t_{1/2,u}$, $AUC_{0-inf,u}$, $CL/F,u$, and $Vd/F,u$) may not be presented as judged appropriate and in accordance with Celerion SOPs.

6.5.3 Urine Pharmacokinetic Parameters

The following PK parameters will be calculated from urine LOXO-292 data using SAS® Version 9.3 or higher. All urine PK parameters included in the protocol are listed in Table 6.3 below, and are defined as appropriate for study design.

Table 6.3. Noncompartmental Urine Pharmacokinetic Parameters to be Calculated for LOXO-292

Label to be Used in Text, Tables and Figures	Definition	Method of Determination
Aet _{1-t2}	Amount of unchanged LOXO-292 excreted during urine collection interval from t ₁ to t ₂ ; the collection CCI [REDACTED]	Calculated as: Urine LOXO-292 concentration * urine volume Note: If the amount of urine excreted was captured in the CRF as urine weight (g), it will be converted to volume (mL) using the assumed density of 1 g/mL.

Label to be Used in Text, Tables and Figures	Definition	Method of Determination
Ae0-t	Total amount of LOXO-292 excreted unchanged in the urine over the entire urine collection period (0-t hours)	Calculated as: The sum of the individual $Ae(t_1-t_2)$ (urine LOXO-292 concentration * urine volume) over the entire urine collection interval Note: If the amount of urine excreted was captured in the CRF as urine weight (g), it will be converted to volume (mL) using the assumed density of 1 g/mL.
CLR	Renal clearance	Calculated as: $Ae(t_1-t_2)/AUC(t_1-t_2)$ Where t_1-t_2 is the longest interval of time during which Ae and AUC are both obtained.
Fe	The percent of dose excreted unchanged into urine from time 0 to the time at the end of the urine collection interval	Calculated as: $100 * [Ae0-t]/Dose$ Where Ae0-t is the cumulative amount of LOXO-292 excreted unchanged in the urine over the entire urine collection period (0-t hours) and dose is the dose of the free base LOXO-292

For the calculation of the urine PK parameters, urine data BLQ concentrations will be treated as 0. See [Section 6.6](#) for further information on missing urine data.

6.6 Data Summarization and Presentation

All LOXO-292 PK concentrations and PK parameters descriptive statistics will be generated using SAS® Version 9.3 or higher.

The total and unbound plasma concentrations of LOXO-292 will be listed and summarized by cohort and time point for all subjects in the PK Population. For the protein binding assay, the buffer chamber (BC) and plasma chamber (PC)

concentrations, % recovery, and fraction unbound will be listed and summarized by cohort for all subjects in the PK Population. The urine concentrations of LOXO-292 will be listed and summarized by cohort and collection-intervals for all subjects in the PK Population.

Plasma and urine concentrations of LOXO-292 will be presented with the same level of precision as received from the bioanalytical laboratory. Unbound plasma concentrations of LOXO-292 will be presented with the same level of precision as received from the bioanalytical laboratory. Data from the protein binding assay will be presented with the same level of precision as received from the bioanalytical laboratory.

Summary statistics, including sample size (n), arithmetic mean (Mean), standard deviation (SD), coefficient of variation (CV%), standard error of the mean (SEM), minimum, median, and maximum will be calculated for all nominal concentration time points and collection intervals. Excluded subjects will be included in the concentration listings, but will be excluded from the summary statistics and noted as such in the tables. All BLQ values will be presented as “BLQ” in the concentration listings and footnoted accordingly.

Mean and individual total and unbound plasma concentration-time profiles will be presented on linear and semi-log scales. Linear mean plots will be presented with and without SD. Urine data will be graphically summarized with mean and individual cumulative amounts of LOXO-292 excreted (Ae0-t) and cumulative % dose excreted unchanged versus end of collection interval, on linear plots (with and without SD for mean).

Total and unbound plasma LOXO-292 PK parameters will be listed and summarized by cohort for all subjects in the PK Population. PK parameters will be reported to 3 significant figures for individual parameters, with the exception of Tmax and t_{1/2}, which will be presented with 2 decimal places. Summary statistics (n, Mean, SD, CV%, SEM, minimum, median, maximum, geometric mean [Geom Mean], geometric CV% [Geom CV%], and 95% CI Geom Mean [presented for AUC0-t, AUC0-inf and Cmax only]) will be calculated for total and unbound plasma LOXO-292 PK parameters. Excluded subjects will be listed in the PK parameter tables, but will be excluded from the summary statistics and noted as such in the tables.

For urine data, in cases where a subject was unable to void during a given interval, the urine volume for that interval will be set to zero, labeled as “UTV” (i.e., “unable to void”), and footnoted accordingly. All urinary parameters requiring volume in their calculation, for that interval only, will be set to zero. The cumulative amount excreted for that interval will be calculated as the previous cumulative amount plus 0. If a sample was collected, but volume was not recorded or only a partial volume was recorded, the urine volume for this that interval will be set to missing and footnoted accordingly. All urinary parameters requiring volume in their calculation, for that interval only, will be set to missing. The cumulative amount excreted for that interval

and all intervals thereafter, including the total cumulative amount excreted, are not calculable and will be set to missing. With the exception of those parameters set to missing, no parameters will be excluded from summary statistics. Furthermore, only results up to the missing interval will be included in summary statistics and in presentation of cumulative urinary excretion plots. Urine concentration results from and beyond the missing interval will be listed in the table and summarized accordingly.

The level of precision for each concentration and PK parameter statistic will be presented as follows:

- minimum/maximum in same precision as in bioanalytical data and parameter output,
- mean/median/Geom Mean in one more level of precision than minimum/maximum,
- SD/SEM in one more level of precision than mean/median/Geom Mean,
- n will be presented as an integer, and
- CV%/ Geom CV% will be presented to the nearest tenth.
- 95% CI Geom Mean will be presented with 2 decimals.

6.7 Statistical Analysis of PK Parameters

6.7.1 Primary Analysis

A comparison of natural-log (ln)-transformed PK parameters (total: AUC0-t, AUC0-inf, and Cmax, and unbound: AUC0-t,u, AUC0-inf,u, and Cmax,u) will be made to evaluate the effect of renal function group on the PK of a single dose of LOXO-292. Since the comparison groups of subjects are independent in terms of degrees of RI and dependent based on the matching criteria, paired t-tests will be performed, using PROC TTEST of SAS®, to assess the differences in PK parameter between each hepatic impairment group versus the corresponding healthy matched control group with respect to 1 to 1 matching. Geometric mean ratios (GMRs) and ninety percent (90%) confidence intervals (CIs) for the ratios will be derived by exponentiation of the mean difference and the CIs obtained for the difference in mean between each renal function cohort and the matching healthy control group.

The paired t-test analysis for each PK parameter will be performed using the following SAS® code for each renal function cohort and its corresponding healthy matched control group:

CCI

CCI

RUN;

Programmer note: The paired t-test will be performed for each renal function group and the subset of corresponding healthy matched control subjects separately. LPKri refers to the set of ln-transformed PK parameters for the subjects in the renal impaired function group of interest (i.e., Mild, Moderate, or Severe) and LPKhealthy refers to the ln-transformed PK parameters for the set of corresponding matching healthy control subjects.

6.7.2 Analysis of Covariance

An analysis of covariance (ANCOVA) will also be performed on the ln-transformed PK parameters (total: AUC0-t, AUC0-inf, and Cmax, and unbound: AUC0-t,u, AUC0-inf,u, and Cmax,u) of LOXO-292 to evaluate the effect of various degrees of RI on the PK of LOXO-292. The ANCOVA model will contain a categorical factor of population for subjects with various degrees of RI (mild, moderate, severe, and healthy matched control subjects), a categorical covariate (sex), and continuous covariates (age and BMI).

Ratios of least-squares means (LSMs) and 90% CIs of ratios will be calculated using the exponentiation of the difference between two cohort LSMs and the corresponding CIs from the ANCOVA analyses on the ln-transformed AUC0-t, AUC0-inf, and Cmax and the corresponding unbound parameters, AUC0-t,u, AUC0-inf,u, and Cmax,u. These ratios will be expressed as a percentage relative to the healthy matched control cohort. Geometric LSM, GMRs, and 90% CIs will be presented.

The ANCOVA analysis will be performed using the following SAS® code:

CCI

Programmer Note: The coefficients in the estimate statements presented above assume that the following decodes will be used for cohort in the database: Mild RI = A, Moderate RI = B, Severe RI = C, Healthy Matched Control = D. Please confirm these coefficients with the Biostatistician prior to data analysis.

6.7.3 Additional Analysis

The relationship between LOXO-292 PK parameters (i.e., Cmax and AUC, total and unbound) and measures of renal function (such as eGFR and CLcr) will be examined in an exploratory manner via a graphically linear regression approach. The PK parameters will be the dependent variable and show on y-axis and measurements for renal impairment will be independent variables and show on the x-axis. The regression equation with slope and intercept, the r-square, and the p-value for slope will be presented in the graphs as footnotes.

If data permits and judged necessary, an exploratory analysis will be performed to assess the relationship between LOXO-292 PK and renal impairment and the effect of covariates (age, BMI, and gender) using an appropriate approach.

7. SAFETY

No inferential statistics are to be performed for the safety analysis.

All clinical safety and tolerability data will be listed by cohort, subject and assessment time points, chronologically. This will include unscheduled assessments (including rechecks) and ET records.

Continuous variables will be summarized using n, mean, SD, minimum, median, and maximum. Frequency counts will be reported for categorical data when appropriate. The level of precision will be presented as follows: “n” as an integer, minimum/maximum in same precision as in the database, mean/median in one more precision level than minimum/maximum, and SD in one more precision level than mean/median. Where individual data points are missing because of dropouts or other reasons, the data will be summarized based on reduced denominators.

When change from baseline is calculated, baseline is the last scheduled or unscheduled assessment before dosing on Day 1, whichever is later. Unscheduled assessments and ET measurements taken after dosing will not be used in the summarization.

Note: The term ‘unscheduled’ assessment used in this SAP may also refer to recheck assessments.

7.1 Subject Discontinuation

Subjects will be summarized by the number of subjects enrolled, completed, and discontinued from the study with discontinuation reasons by cohort and overall. Discontinuation data will be listed by-subject.

7.2 Demographics

Descriptive statistics will be calculated for continuous variables (age, weight, height, and body mass index) by cohort and over all the study. Weight, height and body mass index are summarized at screening. Age will be derived from the date of birth to the date of dosing. Frequency counts will be provided for categorical variables (race, ethnicity, and sex) by cohort and over all the study. A by-subject listing will also be provided.

7.3 Adverse Events

All AEs occurring during this clinical trial will be coded using the Medical Dictionary for Regulatory Activities (MedDRA®), Version 21.1.

Each AE will be graded, by the clinical site, on the National Institution of Health's Common Terminology Criteria for Adverse Events (CTCAE, version 5.0) 5-point severity scale (Grade 1, 2, 3, 4 and 5). Not all grades are appropriate for all AEs. Therefore, some AEs are listed within the CTCAE with fewer than 5 options for grade selection.

The following clinical descriptions of severity for each AE are based on the following general guideline [\[CTCAE Nov2017\]](#):

Table 7.3: Adverse Event Severity Level and Description

Grade	Description
Grade 1	Mild; asymptomatic or mild symptoms; clinical or diagnostic observations only; intervention not indicated.
Grade 2	Moderate; minimal, local or noninvasive intervention indicated; limiting age-appropriate instrumental activities of daily living (ADL)*.
Grade 3	Severe or medically significant but not immediately life-threatening; hospitalization or prolongation of hospitalization indicated; disabling; limiting self-care ADL**.
Grade 4	Life-threatening consequences; urgent intervention indicated.

Grade	Description
Grade 5	Death related to AE.

* Instrumental ADL refer to preparing meals, shopping for groceries or clothes, using the telephone, managing money, etc.

** Self-care ADL refer to bathing, dressing and undressing, feeding self, using the toilet, taking medications and not bedridden.□

Similarly, the causal relationship of the study drug to the AE will be described as Related or Not related to study drug (LOXO-292). All AEs captured in the database will be listed in by-subject data listings including verbatim term, coded term, cohort, severity grade, relationship to study drug, and action; however, only treatment-emergent AEs (TEAEs) will be summarized.

A TEAE is defined as an undesirable event not present prior to medical treatment, or an already present event that worsens either in intensity or frequency following the treatment. Each TEAE will be attributed to the treatment based on Investigator (or designee) judgment as well as on its onset date and time. If an AE has a change in severity grade, the original AE will be given a resolution date and time of the time of severity grade increase or decrease and a new AE record will be initiated with the new severity grade, and the new AE record will use the resolved date/time of the previous record as the onset date/time. If the severity grade of an AE remains the same, the AE will be kept open through to resolution.

If the onset date and/or time of an AE is/are missing, the AE will be treated as a TEAE, unless the onset date of the AE is known to have occurred prior to dosing. TEAEs will be tabulated by system organ class and preferred term. Summary tables will include the number of subjects reporting the AE and as a percent of the number of subjects dosed by cohort and overall. In addition, the number of AEs will be summarized. For an AE with multiple changes in severity, a new record with severity less or equal to its maximum severity will not be included in the adverse event summary tables. Tables will also be presented by severity grade and relationship to study drug. If a subject experienced the same TEAE at more than once with different level of severity grade, only the most severe one will be counted. Similarly, if a subject experienced the same TEAE more than once with different level of drug relationship, only the one most closely related to the study drug will be counted.

Should any serious adverse events (SAEs) occur during the study, the SAEs will be displayed in a table and a narrative included in the Clinical Study Report.

7.4 Clinical Laboratory Tests (Serum Chemistry, Hematology, Coagulation, and Urinalysis)

All clinical laboratory test results will be presented in by-subject data listings, however, only serum chemistry, hematology, coagulation and urinalysis values will be summarized. Given that this study was conducted at multiple sites, by-subject data listings will be provided in conventional units and international system of units (SI units). Summary tables will be provided in SI units.

Hematology, coagulation, serum chemistry and urinalysis tests will be conducted at the following time points:

Table 7.4 Lab Test Time Points

Day
Screening*
Day -1*
Day 2
Day 5
Day 8**

* performed following a fast of at least 12 hours
** performed at EOT or prior to ET

Out-of-normal range flags will be presented in the clinical laboratory listings as recorded in the database. The reference ranges used during the study will be provided in conventional and SI units by study site in Appendix 16.1.10.1. Out-of-range values and unscheduled results will be listed. Results that are indicated as CS by the PI (either in the PI flag or in PI comments) will be listed in the table.

For all laboratory values that are numeric, descriptive statistics (n, mean, SD, minimum, median, and maximum) will be presented for each laboratory test by cohort and time point. Change from baseline will also be summarized. Postdose unscheduled assessments and ET results will not be summarized.

For each laboratory test, a shift table will be developed comparing the frequency of the results at baseline (above normal, normal, or below normal) to postdose results. For urinalysis tests, the categories are normal and outside normal.

Baseline is the last non-missing predose measurement prior to dosing (Day -1), including unscheduled assessments.

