Potential effects of LOXO-292 on the central nervous system were evaluated as part of the GLP 28-day repeat-dose study in rats, in functional observational battery tests and locomotor activity assessments. Findings were limited to animals receiving the high dose on week 4 of the dosing phase, and were attributed to poor general body condition and weight changes associated with LOXO-292 administration rather than specific neurological effects. Additionally, no microscopic abnormalities in neuronal tissues were found.

In toxicology studies of LOXO-292 that were conducted in the rat and minipig, the primary pathologic findings for both species were in the tongue, pancreas, bone marrow and lymphoid tissues; while the gastrointestinal tract and ovaries were target tissues in minipig. Other target tissues identified in the rat included: multi-tissue mineralization, physeal cartilage, incisor teeth, lung, Brunner's gland, and possibly liver. Assessment of doses

associated with moribundity/death revealed a steep dose response curve for both species. LOXO-292 was not mutagenic in the GLP bacterial mutation assay. When evaluated in two in vitro assays, LOXO-292 was not genotoxic. LOXO-292 was not found to be phototoxic when evaluated in an in vitro neutral red uptake phototoxicity assay.

Based on preclinical pharmacology experiments with human cancer cells in vitro and in murine xenograft models, meaningful inhibition of RET in tumors is expected to be achievable with oral dosing regimens **CCI**

Based on the nonclinical profile, including results from animal toxicology studies, theoretical risks of human exposure to LOXO-292 include the following: loss of appetite, decrease in body weight, increase in total white blood cells, neutrophils, and monocytes, decrease in albumin, increase in globulin, decreased albumin:globulin ratio, decrease in total protein, increased body temperature, lethargy, increase in cholesterol and triglycerides, increase in phosphorus, changes in taste sensation and/or development of xerostomia, gastrointestinal symptoms/signs: nausea, vomiting, loose stools, abdominal discomfort, decreases in red cell mass (red blood cell, hemoglobin, hematocrit) and reticulocytes, decrease in platelets, increases in liver function tests (alkaline phosphatase, aspartate aminotransferase, and alanine aminotransferase) and possible pancreas injury.

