12.1.1 All Subjects

1. Male or female (of non-childbearing potential only), 18-70 years of age, inclusive, at Screening.
2. Body mass index (BMI) ≥ 18.0 and $\leq 40.0 \text{ kg/m}^2$ at Screening and have a minimum weight of at least 50 kg at Screening.
3. Female of non-childbearing potential must have undergone one of the following sterilization procedures at least 6 months prior to dosing:
 - hysteroscopic sterilization;
 - bilateral tubal ligation or bilateral salpingectomy;
 - hysterectomy;
 - bilateral oophorectomy;

or be postmenopausal with amenorrhea for at least 1 year prior to dosing and follicle-stimulating hormone (FSH) serum levels consistent with postmenopausal status. Postmenopausal status will be confirmed with a screening serum follicle-stimulating hormone level value within the CRU's laboratory's expected range for post-menopausal status. All females must have a negative qualitative serum pregnancy test (serum human chorionic gonadotropin) at Screening and Check-in (Day -1).

4. Males who are capable of fathering a child must agree to use one of the following methods of contraception from the time of the dose administration through 6 months after the study drug administration on Day 1.

Male sterilization, with documented confirmation of surgical success. Male subjects will be surgically sterile for at least 90 days prior to Check-in (Day -1). If documentation is not available, male subjects must follow one of the contraception methods below:

- a. Male condom with spermicide, and
- b. For a female partner of male study participant:
 1. Intrauterine device (IUD) (hormonal IUD; e.g., Mirena[®]).
Copper IUDs are acceptable (e.g., ParaGard[®]);
 2. Established use of oral, implanted, transdermal, or hormonal method of contraception associated with inhibition of ovulation; or
 3. Bilateral tubal ligation.

Males who practice true abstinence because of a lifestyle choice (i.e., do not become abstinent just for the purpose of study participation) are exempt from contraceptive requirements. Periodic abstinence by a female partner (e.g., calendar, ovulation, symptothermal, postovulation methods) and withdrawal are not acceptable methods of contraception. If a male subject is abstinent at the time of signing the ICF but becomes sexually active during the study, he must agree to use contraception as described above.

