12.1.2 Additional Requirements for Subjects with RI

1. Subject is a non-smoker or moderate smoker and is willing to consume no more than 5 cigarettes/day or equivalent in tobacco or nicotine-containing products from Check-in (Day -1) through EOT or ET and refrain from the use of tobacco or nicotine containing products for 2 hours prior to dosing and 4 hours after dose administration on Day 1.

2. With the exception of renal insufficiency, baseline medical health is judged to be stable with no clinically significant medical history, physical examination, laboratory profiles, vital signs, or ECG abnormalities, at Screening and at the time of Check-in (Day -1), as deemed acceptable by the PI (or designee), with agreement from the Celerion Medical Monitor and the Sponsor.
3. Liver function tests (alanine aminotransferase [ALT] and aspartate aminotransferase [AST]) and serum (total and direct) bilirubin, amylase and lipase should be within the upper limit of normal, for the laboratory used by the CRU at Screening and Check-in (Day -1). Rechecks of the LFTs (ALT and AST), serum (total and direct) bilirubin, amylase and lipase will be permitted up to 2 times to confirm subject eligibility. Subjects may be eligible for participation in the study based on rechecked values if these values are within the upper limit of normal or if these values are consistent with their renal disease and if the PI (or designee), with agreement from the Celerion Medical Monitor and the Sponsor, feels that the results are not clinically significant, and will not impact study conduct.
4. Subject is not currently or has not previously been on hemodialysis.
5. Baseline eGFR based on the MDRD equation at Screening as follows:
 - Severe RI: $< 30 \text{ mL/min/1.73m}^2$
 - Moderate RI: $\geq 30 \text{ and } < 60 \text{ mL/min/1.73m}^2$
 - Mild RI: $\geq 60 \text{ and } < 90 \text{ mL/min/1.73m}^2$

The MDRD equation is as follows (for females multiply result by 0.742, if African American multiply result by 1.212):

$$\text{eGFR} = 175 \times (\text{S}_{\text{cr, std}})^{-1.154} \times (\text{Age})^{-0.203}$$

$\text{S}_{\text{cr, std}}$: serum creatinine (mg/dL) measured with a standardized assay.

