Note: Baseline is the last non-missing predose measurement prior to dosing (Day -1), including unscheduled assessments.

All subjects received a single oral dose of 160 mg LOXO-292 following a 2-hour fast.

Cohort Descriptions: <description>

SCI

DDMMYYYY HH:MM

Tables 14.3.5.3, 14.3.5.6, and 14.3.5.9 will have the following format:

Page 1 of X

Table 14.3.5.3 Clinical Laboratory Shift from Baseline - Serum Chemistry (Safety Population)

Laboratory Test (units)	Cohort	Time Point	Baseline L			Baseline N			Baseline H		
			Postdose			Postdose			Postdose		
			L	N	H	L	N	H	L	N	H
Testname(unit)	Mild	Day 2	X	XX	X	X	XX	X	X	XX	X
		Day 5	X	XX	X	X	XX	X	X	XX	X
		Day 8	X	XX	X	X	XX	X	X	XX	X

Programmer note: Similar for remaining laboratory tests. Use N = Within Normal Range, O = Outside Normal Range for urinalysis shift table.

Note: N = Within Normal Range, L = Below Normal Range, H= Above Normal Range.

Baseline is the last non-missing predose measurement prior to dosing (Day -1), including unscheduled assessments.

All subjects received a single oral dose of 160 mg LOXO-292 following a 2-hour fast.

Cohort Descriptions: <description>

CCI

DDMMYYYY HH:MM

Tables 14.3.5.10 and 14.3.5.11 will have the following format:

Page 1 of X

Table 14.3.5.10 Vital Sign Summary (Safety Population)

Vital Sign Parameter (unit)	Time Point	Statistic	Cohort			
			Mild	Moderate	Severe	Healthy
Parameter1 (unit)	Screening	n	X	X	X	X
		Mean	X.X	X.X	X.X	X.X
		SD	X.XX	X.XX	X.XX	X.XX
		Minimum	XX	XX	XX	XX
		Median	X.X	X.X	X.X	X.X
		Maximum	XX	XX	XX	XX
	Day -1	n	X	X	X	X
		Mean	X.X	X.X	X.X	X.X
		SD	X.XX	X.XX	X.XX	X.XX
		Minimum	XX	XX	XX	XX
		Median	X.X	X.X	X.X	X.X
		Maximum	XX	XX	XX	XX
	Day 1 Predose	n	X	X	X	X
		Mean	X.X	X.X	X.X	X.X
		SD	X.XX	X.XX	X.XX	X.XX
		Minimum	XX	XX	XX	XX
		Median	X.X	X.X	X.X	X.X
		Maximum	XX	XX	XX	XX

<Programmer note: Similar for remaining vital sign parameters and time points. For the change from baseline tables, please remove the screening, Day -1, and Day 1 Predose time points, keep the baseline definition footnote and change the 'Cohort' header to 'Change From Baseline'.

Note: Baseline is the last non-missing predose measurement prior to dosing (Day 1 Predose), including unscheduled assessments. All subjects received a single oral dose of 160 mg LOXO-292 following a 2-hour fast.
Cohort Descriptions: <description>

CCI

DDMMYYYY HH:MM

Tables 14.3.5.12 and 14.3.5.13 will have the following format:

Page 1 of X

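### The low/normal/high shift table cannot show a creatinine rise in severe renal impairment, or in many moderate subjects, so its creatinine counts cannot be compared across cohorts

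*SAP*

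**What the plan says.** SAP 7.4 sets one shift format for every laboratory test: "a shift table will be developed comparing the frequency of the results at baseline (above normal, normal, or below normal) to postdose results". Urinalysis is the only exception, with normal and outside normal. The shell for Table 14.3.5.3 is a three-by-three grid by cohort at Days 2, 5 and 8, with the key "N = Within Normal Range, L = Below Normal Range, H= Above Normal Range". It has no category for size of change or for toxicity grade. The limits are those of each site: "The reference ranges used during the study will be provided in conventional and SI units by study site", in Appendix 16.1.10.1. Their values are not in the documents.

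The same section plans other laboratory displays:
- "descriptive statistics (n, mean, SD, minimum, median, and maximum) will be presented for each laboratory test by cohort and time point";
- change from baseline (Table 14.3.5.2 for serum chemistry);
- a by-subject listing of out-of-range and unscheduled values (Table 14.3.4.1);
- a table giving all time points for any subject and test with a value that the investigator calls clinically significant (Table 14.3.4.4).

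Protocol 12.1.2 defines severe impairment as MDRD eGFR below 30, moderate as 30 to below 60 and mild as 60 to below 90 mL/min/1.73 m². Serum creatinine is the only laboratory input to that equation.

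**The concern.** A shift table counts subjects who cross a limit. If a cohort is selected so that all its members already lie beyond the limit, the count of upward crossings is zero before any data arrive. A severe subject whose creatinine doubles is recorded as high-to-high, while a control whose value moves just past the limit is recorded as a shift.

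Safety in subjects with renal impairment is a secondary objective. Read across the columns, the table could show normal-to-high creatinine shifts in controls and none in the severe cohort. That pattern would look like renal stability in the most impaired subjects but would say nothing about it.

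**Working it through.** The plan gives no figure to reproduce. The check is to find the creatinine that each entry criterion implies and to compare it with plausible upper limits of normal (ULN).

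**Inputs.** From Protocol 12.1.2: eGFR = 175 × Scr^(−1.154) × Age^(−0.203), with the adjustment "for females multiply result by 0.742, if African American multiply result by 1.212". From Protocol 12.1.1: "18-70 years of age, inclusive, at Screening". Assumed, because the documents give no limits: ULN 1.2 to 1.4 mg/dL in men and 0.9 to 1.2 in women.

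**Inverted formula.** Scr = [175 × Age^(−0.203) × (0.742 if female) × (1.212 if African American) / eGFR]^(1/1.154). Implied creatinine falls with age and is lowest in women without the 1.212 factor.

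**Severe (eGFR below 30).** The lowest case is a non-African American woman aged 70. Here 70^(−0.203) = 0.422 and 175 × 0.422 × 0.742 = 54.8, so (54.8/30)^(1/1.154) = 1.69 mg/dL. Men start above 2.18 to 3.28 mg/dL, depending on age and the race factor. All of these exceed 1.4.

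The shift baseline is the last predose value, nominally Day −1, and not the value used for cohort assignment. If eGFR rose by 20% in between, to 36, the lowest case becomes (54.8/36)^(1/1.154) = 1.44 mg/dL, still above the assumed range.

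**Moderate (30 to below 60).** The eGFR at which creatinine equals the ULN is e* = 175 × ULN^(−1.154) × Age^(−0.203) × factors. If eGFR is uniform within the band (an assumption), the share starting high is (e* − 30)/30, limited to 0 to 100%. At ages 40, 60 and 70:
- Men, ULN 1.2 to 1.4: 67% to 100%. The lowest case is age 70, ULN 1.4, non-African American: e* = 50.1, and (50.1 − 30)/30 = 67%.
- Women, ULN 0.9 to 1.2: 48% to 100%. The lowest case is age 70, ULN 1.2, non-African American: e* = 44.4, and (44.4 − 30)/30 = 48%. No other combination falls below half.

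**Mild (60 to below 90), age 60.** The share starting high is (e* − 60)/30, on the same uniform assumption.

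| Assumed ULN (men / women) | Non-African American (men / women) | African American (men / women) |
|---|---|---|
| 1.3 / 1.1 | 0% / 0% | 27% / 5% |
| 1.2 / 0.9 | 6% / 13% | 50% / 58% |

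Most mild subjects can therefore shift, except possibly African American subjects at sites with low limits.

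**Rise needed to be counted** (age 60, non-African American, ULN 1.3 / 1.1). At eGFR 90, the lower edge for a control, creatinine must rise by about 50% in a man or 65% in a woman. At eGFR 75 (mild) the figures are 28% and 40%. In a severe subject no rise is ever counted. The same table thus applies a different threshold to each cohort.

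**Do the other displays supply the missing count?**
- Change from baseline shows the largest rise at each visit. It does not show how many subjects rose, or by what multiple of their own baseline.
- The out-of-range listing would hold nearly every creatinine value from a severe subject, stable or rising.
- The clinically significant table depends on the investigator's judgement.
- Treatment-emergent events (SAP 7.3) include worsening of an existing condition and are counted by subject and grade. For laboratory values, Protocol 14.2.6.2 makes this too depend on a judgement of clinical significance.

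**The case against.** The strongest reply is that this is a limit of one descriptive table in a single-dose study with up to eight subjects per impaired cohort. SAP section 7 plans no safety inference, and no decision rule uses the shift table. A doubling of creatinine in a severe subject would appear as the maximum change from baseline and in the listings. If judged clinically significant, it would also appear in Table 14.3.4.4 and among the counted adverse events. All of this stands, and it sets the weight of the point.

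A reader might infer three stronger things that the documents do not support.
- **That worsening is invisible in renal impairment and visible only in controls.** Most mild subjects start within normal and need a smaller relative rise than a control to be counted. Some moderate subjects also start normal.
- **That the same holds for urea nitrogen, potassium, phosphorus and uric acid.** No entry criterion places these above normal, and no baseline values are given. Phosphorus matters for another reason: the theoretical risks in Protocol 9.1.1 include "increase in cholesterol and triglycerides, increase in phosphorus". Creatinine is not on that list.
- **That the laboratory shift tables fail as a whole.** ALT, AST, bilirubin, amylase and lipase should be within the upper limit at entry in impaired subjects, with an exception on recheck (Protocol 12.1.2), so their shift tables generally work.

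The reply does not answer one thing. No planned display counts, by a fixed rule, the subjects in each cohort whose creatinine rose from their own baseline.

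**Conclusion.** The point holds for creatinine in this one display. In the severe cohort the number of possible upward shifts is zero for any ULN from 0.9 to 1.4 mg/dL, so that result does not depend on the choice of limit. In the moderate cohort a large share is affected, from about half to all on the limits tried. That figure rests on the assumed limits and on a uniform spread of eGFR within the band. Because controls and most mild subjects can shift, a comparison of creatinine shifts between cohorts is uninformative by construction.

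This is an inexpensive improvement to the safety reporting. It does not mean that a creatinine rise would go unreported, and it has no bearing on the primary PK comparison.

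**What to change.** For serum creatinine, add to the low/normal/high shift, or replace it with, the number of subjects per cohort by highest scheduled postdose value (Days 2, 5 and 8) divided by the subject's own baseline. Fix the cut-points in advance, for example up to 1.25 times, above 1.25 to 1.5 times, and above 1.5 times. These are illustrative and have no source in the documents. Using scheduled visits matches SAP 7.4, which leaves postdose unscheduled and early-termination results out of the summaries; those values stay in the listings.

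A ratio is safer than a baseline-to-worst CTCAE grade. The documents give only the general grading guideline and no laboratory grade limits, so they cannot show that grading removes the ceiling.

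The same format may be applied to phosphorus, or to any analyte found to be mostly above normal at baseline in an impaired cohort. Keep low/normal/high for all other tests.

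The cost is one more table format and cut-points that the sponsor must agree. No new data are needed. If the laboratory tables have already been produced, the CSR should record the addition as a change from plan.
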